7.1 Anticipated Clinical Benefits

The information obtained from participation in the study will potentially be useful to the participating subjects, the Sponsor as well as future candidates and health care providers in better understanding the potential benefits of cochlear implantation on hearing handicap, communicative function, loneliness, mental wellbeing, and cognitive functioning.

7.2 Anticipated Adverse Device Effects

Known anticipated adverse device effects are currently detailed in the Cochlear Nucleus® Profile™ Slim Modiolar (532) cochlear implant or the Cochlear Nucleus® Profile™ Plus CI632 cochlear implant with Slim Modiolar electrode Physician's Guide (17). There are no additional anticipated adverse device effects related to participation in this clinical study. The surgeon will conduct the surgical procedure as per standard clinical practice and individuals will be exposed only to the normal risks associated with routine cochlear implantation.

7.3 Residual risks related to the use of the investigational device

The study does not involve use of an investigational device.

7.4 Risks associated with participation in the clinical investigation

Participation in this study does not include any additional risks to those known for individuals undergoing neurocognitive evaluations, cochlear implantation or hearing aid use clinically. The risks associated with each procedure will be outlined in the Informed Consent (IC) document. All risks should be thoroughly reviewed with the potential subject prior to participation in the study.

7.5 Possible interactions with concomitant medical treatments

There is potential that concomitant medical treatments may influence the outcomes of this study. All concomitant medical treatments will be collected as part of this study.

7.6 Risk mitigations

The investigators or qualified delegates will be required to review the terms of the Informed Consent with each potential subject. Information such as the subject's ongoing audiology and medical history will be captured for the duration of the trial.

7.7 Risk to benefit rationale

Since the participants recruited for this study are already considering cochlear implantation as a hearing health option, the risk benefit rationale is such that participation in this study may provide subjects with additional useful health information pertaining to their cognitive status that they would not otherwise have.

8 OBJECTIVES AND HYPOTHESES

8.1 Primary Objective

To determine the effect of treating hearing loss with cochlear implantation (CI) versus continued use of hearing aids (HA) on hearing satisfaction using the Speech, Spatial and Qualities of Hearing (SSQ12) in older adults.

8.2 Secondary Objectives

To assess cognition in older adults with hearing loss with a Cogstate® battery of neuropsychological tests.

8.3 Primary Hypotheses

Cochlear implantation is associated with greater reduction on hearing satisfaction as measured using the Speech, Spatial and Qualities of Hearing (SSQ12) compared to continued hearing aid use at Follow-up Visit 1 (FUV1).

9 DESIGN OF THE CLINICAL INVESTIGATION

9.1 General

9.1.1 Primary Endpoint

Assessment of the impact of cochlear implantation versus continued hearing aid use on hearing satisfaction as measured using the Speech, Spatial and Qualities of Hearing (SSQ12) at Follow-up Visit 1 (FUV1).

9.1.2 Secondary Endpoints

Assessment of the impact of cochlear implantation versus continued hearing aid use on cognition with a Cogstate® battery of neuropsychological tests on at Follow-up Visit 1 (FUV1).

9.2 Assessments

9.2.1 Neuropsychological Test Battery

9.2.1.1 Hearing Impaired Montreal Cognitive Assessment (HI-MoCA)

The Montreal Cognitive Assessment (MoCA) is an interviewer administered screening tool used to detect mild cognitive impairment (18). It has been demonstrated to have high sensitivity and specificity for detecting mild cognitive impairment (18-20). The MoCA has been used in clinical evaluations to assess cognitive function and treatment effect in older patients undergoing cochlear implantation (21, 22). The MoCA has been converted into a timed PowerPoint (Microsoft Corp., Redmond, WA) presentation, and verbal instructions converted into visual instructions to assist in the assessment of severely hearing impaired adults - the Hearing Impaired Montreal Cognitive Assessment (HI-MoCA) (23). The HI-MoCA has been validated as a screening for cognitive impairment in the severely hearing impaired older populations. No conversion factor from HI-MoCA to MoCA scores were required in the cohort of cognitively intact subjects. The HI-MoCA will be used in the clinical investigation to assess cognitive function of older adults undergoing cochlear implantation.

9.2.1.2 Cogstate computerised test battery

The Cogstate® computerised test battery is a self-administered, iPad-based neuropsychological measure of processing speed, attention, visual learning, working memory and executive function. The Cogstate computerised test battery for the current clinical investigation consists of the Cogstate Brief Battery™ and the Groton Maze Learning Test.

The Cogstate Brief Battery (CBB) provides a measure of four core cognitive domains: processing speed, attention, visual learning and working memory. The CBB consists of the Detection Test, Identification Test, One Card Learning Test and One Back Test. The Detection test measures processing speed using a simple reaction time paradigm. The Identification test measures attention using a choice reaction time paradigm. The One Card Learning test measures visual memory using a pattern separation paradigm. The One Back test measures working memory using an n-back paradigm. For all tests in the CBB, a playing card is presented on the screen and the participant is encouraged to work as quickly as they can and be as accurate as possible.

The Cogstate Groton Maze Learning Test measures executive function using a maze learning paradigm. A 28-step pathway is hidden among these tiles. The participant must move one step at a time from the start toward the end by touching a tile next to their current location. If the correct move is made a green checkmark appears and if the move is incorrect a red cross is revealed. Once completed, they are returned to the start location to repeat the test and must try to remember the

pathway they have just completed. The outcome measure is the total number of errors made in attempting to learn the same hidden pathway on five consecutive trials during a single session.

9.2.2 Verification of Hearing Aid Fitting

Real ear insertion gain measurements (REIG) will be used to verify hearing aid fitting. The frequency response of the hearing aid should not deviate from the National Acoustic Laboratories' non-linear procedure (NAL-NL2) target by greater than +/- 5 dB for a modulated speech stimulus (International Speech Test Signal (ISTS)), except in circumstances where adjustments have been made for patient comfort/preference or feedback management.

9.2.3 Audiologic Measures

9.2.3.1 Audiometric Thresholds and Tympanometry

9.2.3.1.1 Unaided audiometric thresholds

Unaided audiometric thresholds will be obtained for each ear, with insert earphones, using the standard audiometric technique for pure-tone air-conduction testing. All preimplantation testing will be completed using an audiometer calibrated to American National Standards Institute (ANSI) standards with maximum output for frequencies of 0.5 to 4 kHz of no less than 110 dB HL. Pure tone threshold exploration will be completed using the adaptive Hughson & Westlake procedure (24).

Testing in each ear will include the following:

Air conduction thresholds: 250, 500, 1000, 2000, 4000, 6000, 8000 Hz with appropriate masking as required;

Tympanometry in each ear.

An audiogram completed up to 90 days prior to POV1 will be considered for determination of eligibility and data collection as part of POV1.

9.2.3.1.2 Aided audiometric thresholds

Aided audiometric thresholds will be obtained for the everyday listening condition (aided bilaterally or bimodally post-CI) during a clinical review visit three months post POV2 (+/- 2 weeks), in a calibrated sound field, using the standard audiometric technique for sound field testing. All post-implantation testing will be completed using warble tones in a sound field calibrated to American National Standards Institute (ANSI) standards with maximum output for frequencies of 0.5 to 4 kHz of no less than 80 dB SPL.

Testing in the everyday listening condition (both ears) will include the following:

Aided sound field thresholds: 500, 1000, 2000, 4000 Hz

9.2.3.2 Speech perception in quiet

The CNC Word Test (25) is a validated test used clinically and in research to assess the performance of adults with hearing aids or cochlear implants on open-set word recognition. The test consists of 10 recorded lists of 50 monosyllabic words in CD format. For this study, two lists will be administered in quiet at a level equal to 60 dBA in the sound field and scored as total number of words and phonemes correct, which will be expressed as a percentage correct for this study. Subjects will be tested using a configuration of speech at 0° azimuth in quiet (S0).

9.2.3.3 Speech perception in noise

The AzBio Sentence Test (26) is a validated test used clinically and in research to assess the open-set sentence recognition in speech-weighted noise of adults with hearing aids or cochlear implants. It

consists of 15 lists of 20 sentences each. AzBio sentences are spoken by different talkers in a conversational style with limited contextual cues that the listener can use to predict or 'fill in' unintelligible words. The sentences will be presented at a fixed level of 65 dBA at a fixed +10 dB signal-to-noise ratio (SNR). Each list includes 5 sentences from 4 different male and female speakers. The average level of intelligibility of each list is 85% +/- 1%. Each word in the sentence counts towards the overall score. Subjects will be tested using a configuration of speech and noise at 0° azimuth (S0N0).

9.2.3.4 Hearing Handicap Inventory for the Elderly

The Hearing Handicap Inventory for the Elderly - screening (27) is an interviewer-administered questionnaire that measures the perception of the impact of hearing loss. This questionnaire assesses the social and emotional components of perceived hearing impairment such as embarrassment, and limits on personal and social life.

9.2.3.5 Speech, Spatial, and Qualities of Hearing Scale (SSQ12)

The SSQ is a validated 12-question self-assessment metric commonly used in hearing research, designed to measure auditory disability across a wide variety of everyday world domains. The SSQ-12 (28) has twelve questions and is derived from the original 49 item SSQ (29). In addition to a reduced administration time, the SSQ-12 has been shown to have similar results to the original 49 item scale (28).

9.2.4 Psychosocial Measures

9.2.4.1 UCLA Loneliness Scale

The UCLA Loneliness Scale version 3 (30) is an interviewer-administered questionnaire. The 20-item scale designed to measure one's subjective feelings of loneliness as well as feelings of social isolation. Subjects rate each item on a scale from 1 (Never) to 4 (Often). This measure is a revised version of both the original UCLA Loneliness Scale and the Revised UCLA Loneliness Scale. The first revision was done to make 10 of the 20 original items reverse scored. The second revision was done to simplify the scale so less educated populations could comprehend it.

9.2.4.2 Geriatric Depression Scale (GDS)

The GDS Short Form is an interviewer-administered 15-item questionnaire in which subjects are asked to respond by answering yes or no in reference to how they felt over the past week. Questions from the Long Form GDS which had the highest correlation with depressive symptoms in validation studies were selected for the short version (31). Of the 15 items, 10 indicated the presence of depression when answered positively, while the rest (question numbers 1, 5, 7, 11, 13) indicated depression when answered negatively. Scores of 0-4 are considered normal, depending on age, education, and complaints; 5-8 indicate mild depression; 9-11 indicate moderate depression; and 12-15 indicate severe depression. The GDS Short form has been tested and used with the older population receiving cochlear implants (15, 32-34).

9.2.5 Physical Functioning Measures

9.2.5.1 Lifestyle Activity Questionnaire

The Lifestyle Activity Questionnaire (LAQ) (35) is a self-administered questionnaire which assesses the frequency of self-reported activities over the past year. The questionnaire includes intellectual (e.g. discussing local or national issues, reading), social (e.g. caretaking, clubs), physical (e.g. shopping, gardening), creative (e.g. drawing or painting), and passive (e.g. listening to music, watching TV) activities. The LAQ has been shown to be sensitive to assessing relationships between

cognitively and socially stimulating activities and cognitive aging in both observational studies (35) and in trials (36, 37).

9.2.5.2 Near Vision Screening

The Near Vision Screening chart is an eye chart to measure visual acuity in the near field (within 16"). The first line consists of two very large letters and a number. Subsequent rows have increasing numbers of letters and numbers that decrease in size. A person (with corrected vision) taking the test with holds the card at a distance of 16" under standard room illumination, and reads aloud the letters and numbers of each row, beginning at the top. The smallest row that can be read accurately indicates the visual acuity.

9.2.6 Quality of Life Measure

9.2.6.1 Health-Utilities Index 3

The Health Utilities Index Mark 3 (HUI3) (38, 39) is a widely used self-administered generic instrument measuring health-related quality of life. This instrument covers eight domains (vision, hearing, speech, ambulation, dexterity, emotion, cognition, and pain), each having five or six levels of difficulty. There are 970,000 possible combinations of levels, of which a subset has been evaluated by members of the Canadian general public (39). The HUI3 focuses on physical and emotional wellbeing and includes questions specific to hearing and the ability to be understood whilst speaking. As a result it is sensitive to improvements in quality of life due to better hearing (40-42). This questionnaire follows the principles of economic evaluation in that a utility score is derived where 1 indicates perfect health and zero corresponds to being dead, therefore it can be used in cost-effectiveness analyses.

9.2.7 Medical and Hearing History

9.2.7.1 Medical History via the Adult Comorbidity Evaluation-27 (ACE-27)

Medical history will be collected at Pre-operative Visit 2. The ACE-27 is an index which includes 27 conditions or comorbid ailments across various bodily organ systems. Each of the comorbid ailments are graded on severity (none, mild, moderate, or severe) with the end result of an overall index score. Early research in patients with hearing loss indicated untreated hearing loss resulted in a higher incidence of morbidity compared to individuals with no hearing loss. This index allows for consistent collection of medical history data across subjects and clinical sites. It will be used as a minimum medical history reporting standard for this clinical investigation. Additional medical history may be added at the Investigator's discretion for relevant study conduct.

9.2.7.2 Hearing History

Hearing history will be collected at Pre-operative Visit 1 as outlined on the CRF. Information collected will include duration, type and etiology of hearing loss in addition to hearing aid details (e.g., consistent vs intermittent hearing aid use).

9.3 Methods

9.3.1 Screening and Informed Consent

Subjects who have been deemed appropriate candidates for cochlear implantation according to standard clinical practice will be considered potential research subjects for this study. Informed consent must occur prior to study related activities with the exception of an audiogram performed within 90 days of POV1. Individuals will be appropriately counseled on the risks and benefits of study participation prior to participating in any study related activity. If needed, the potential participant may take the informed consent form home with them for review prior to completion. If the participant

agrees to participate, a copy of the executed informed consent will be provided to the participant. To maintain confidentiality, subject names will not be recorded on any study document other than the informed consent form. All individuals who provide informed consent are considered enrolled into the study and will be assigned a unique identifier. A unique alphanumeric code will identify each subject throughout the course of the study. For example, US01-HOA-xxxx where:

- US = United States
- 01 = a sequential numeral corresponding to the order in which a subject is enrolled into the study for a given study site. In this case this would correspond to the first subject recruited into the study for a particular site
- HOA = an abbreviation for the study, Hearing Loss in Older Adults
- xxxx = a unique numeric study site identification

9.3.2 Randomization

The design of the clinical investigation is a prospective, 1:1 randomized clinical trial. The intervention arm to which a participant is assigned is determined by an allocation schedule developed by [REDACTED]

To ensure balance between the treatment arms, participants will be randomized as described in the Statistical Analysis Plan (D1309522). Block size will not be revealed to field center staff as this would allow them to determine the final treatment assignment of a block before ascertaining eligibility and obtaining consent. The randomization will be maintained by the sponsor within a data management system. Randomization will be performed at POV1.

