9.3.4 Preoperative Visit 1 (POV1) - Screening

Participants are consented into the study. Eligibility for the study will be confirmed. During this preoperative screening visit, each participant will be randomized in a 1:1 ratio to either the immediate CI (Arm A) or hearing aid (delayed CI Arm B). During POV1, both Arm A and Arm B subjects will complete the neuropsychological assessments as described in Section 9.2.1 with appropriately fitted hearing aids and glasses (if required).

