9.3.5 Preoperative Visit 2 (POV2) - Baseline

Preoperative visit 2 (POV2) baseline will occur 4-6 weeks post POV1 (+/- 2 weeks) to enable scheduling of surgery for Arm A subjects. Both Arm A and Arm B subjects will complete POV2 with appropriately fit hearing aids and glasses (if required). The full neuropsychological battery in addition to the audiology, psychosocial, physical, and quality of life metrics will be completed as described in Section 9.2. Speech recognition will be assessed in the everyday listening condition (aided bilaterally) and the ear to be implanted listening conditions with the contralateral ear plugged. Datalogs will be retrieved for the hearing aid.

Medical history will be completed minimally via the ACE 27 index. The Investigator or appropriately delegated staff may add additional otologic history (hearing history) which they deem relevant to the study.

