4.1 Randomization

Subjects will be randomized after eligibility has been confirmed and confirmed that the subject will participate in the clinical investigation. Randomization will be performed using a random permuted block design stratified by field site with a 1:1 allocation ratio (Arm A: immediate cochlear implant vs. Arm B: hearing aid control). If a subject withdraws from the clinical investigation, they will be not be replaced by another subject. The randomization table will account for 20% subject attrition.

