4.2 Blinding

No blinding will be applied in this study.

[figure not shown]
5 Sample Size Determination.

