6.1.2 Visit Windows

Unless otherwise specified, visit assessments will be analyzed for each analysis time point as described in Sections 6.6 and 6.7.

Each test measure by arm/visit abbreviation is described in the table below.

Where:

A = Arm A, B = Arm B, and x = number of months post-baseline measure.

[figure not shown]
Procedure	Screening POV1	Baseline POV2	FUV1	FUV2	FUV3
HI-MoCA	A0 or B0		A6 or B6	A12 or B12	B18
HHIE-S	A0 or B0		A6 or B6	A12 or B12	B18
Cogstate		A0 or B0	A6 or B6	A12 or B12	B18
SSQ12		A0 or B0	A6 or B6	A12 or B12	B18
UCLA		A0 or B0	A6 or B6	A12 or B12	B18
GDS		A0 or B0	A6 or B6	A12 or B12	B18
LAQ		A0 or B0	A6 or B6	A12 or B12	B18
HUI-III		A0 or B0	A6 or B6	A12 or B12	B18
CNC words		A0 or B0	A6 or B6	A12 or B12	B18
AzBio sentences		A0 or B0	A6 or B6	A12 or B12	B18
Audiometric thresholds	A0 or B0		A6 or B6	A12 or B12	B18

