6.6.1.1 Primary Analysis

The primary efficacy endpoint will be assessed with the following hypothesis:

$$H_0: \mu_A \geq \mu_B$$

$$H_a: \mu_A < \mu_B$$

Statistical Analysis Plan		Page 11 of 16
Sponsor Cochlear	Study Hearing Loss in Older Adults	CIP Version 9.0

Where μ_{A6} is the mean SSQ12 score for the cochlear implantation treatment Arm A and μ_{B6} is the mean SSQ12 score for the hearing aid control Arm B at FUV1. The hypothesis will be evaluated using a regression model with treatment and baseline score as covariates. Significance of the treatment effect will be assessed by the p-value for the treatment arm from the regression model.

For analyses using means in the primary endpoints, where there is evidence the model assumptions are not met (e.g. lack of normality of the residuals), transformations or non-parametric tests will be employed.

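### Baseline SSQ12, the covariate in the primary model, is self-reported 2 to 8 weeks after open-label randomisation, so known allocation could shift it and subjects who leave in the gap will lack it

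*Protocol*

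**What the plan says.** **Timing of allocation.** Protocol 9.3.2 states "Randomization will be performed at POV1", and 9.3.4 agrees: "During this preoperative screening visit, each participant will be randomized in a 1:1 ratio". The schedule in Protocol section 5 marks randomisation at POV1. SAP 4.1 says only "Subjects will be randomized after eligibility has been confirmed", which names no visit and does not move randomisation to POV2.

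**Timing of baseline SSQ12.** The same schedule first marks SSQ12 at POV2. The SAP 6.1.2 table places A0/B0 for SSQ12 under POV2 and leaves the POV1 cell empty. Protocol 9.3.5 gives the interval and its purpose: "Preoperative visit 2 (POV2) baseline will occur 4-6 weeks post POV1 (+/- 2 weeks) to enable scheduling of surgery for Arm A subjects".

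**Masking.** SAP 4.2: "No blinding will be applied in this study". Protocol 9.2.3.5 describes SSQ12 as a self-assessment.

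**Use of the score.** SAP 6.6.1.1: "The hypothesis will be evaluated using a regression model with treatment and baseline score as covariates". SAP 6.4 imputes missing SSQ12 using gender, age and baseline. SAP 6.2 puts every randomised subject in the ITT set regardless of withdrawal, and SAP 4.1 does not replace withdrawals.

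**The concern.** A baseline covariate is safe to adjust for because randomisation cannot have influenced it. Here that protection is absent. By POV2 an Arm A subject is about a week from surgery, while an Arm B subject faces roughly six more months with hearing aids. The documents do not say when subjects are told their arm. Nothing conceals it, however, and the interval exists so that Arm A surgery can be booked. Either group might then rate its current hearing differently because of what it knows. Any such difference would pass into the adjusted treatment effect.

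There is also a gap in the ITT analysis. A subject who leaves between POV1 and POV2 belongs to the ITT set but has no baseline SSQ12. The imputation model names baseline as a predictor, and the SAP has no rule for a missing baseline.

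**Working it through.** **1. Gap.** Shortest: 4 − 2 = 2 weeks. Longest: 6 + 2 = 8 weeks.

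**2. Yardstick.** SAP 5.1.1 assumes a mean SSQ12 change of 3.0 (SD 1.8), so d = 3.0/1.8 = 1.667. A two-sample t-test at two-sided α 0.025 and 80% power needs 9 per arm (power 0.844). With 20% attrition, 9/0.8 = 11.25, rounded up to 12, which reproduces the SAP figure. At d = 1.667, power exceeds 0.999 with 28 or even 24 per arm. The issue is therefore bias and ITT handling, not power.

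**3. Bias formula.** The adjusted effect is (Ȳ_A − Ȳ_B) − b(X̄_A − X̄_B), where Y is the FUV1 score, X the baseline score and b the baseline slope. Suppose allocation adds a difference δ (A minus B) to reported baseline without changing the FUV1 rating or the slope. The effect is then biased by −bδ. If Arm A under-reports, the A-minus-B estimate rises; if Arm A over-reports, it falls by the same amount.

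The documents give neither b nor δ, so both are assumed: b = 0.3, 0.5, 0.7 and |δ| = 0.25, 0.5, 1.0 points. Absolute bias in points, with the percentage of 3.0:

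| Slope | Shift 0.25 | Shift 0.5 | Shift 1.0 |
|---|---|---|---|
| 0.3 | 0.075 (2.5%) | 0.15 (5.0%) | 0.30 (10.0%) |
| 0.5 | 0.125 (4.2%) | 0.25 (8.3%) | 0.50 (16.7%) |
| 0.7 | 0.175 (5.8%) | 0.35 (11.7%) | 0.70 (23.3%) |

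**4. Effect on the test.** Simulation used 28 per arm, SD of change 1.8, equal SD at both visits (so the slope equals the correlation), no true effect, two-sided 0.05 and 20,000 runs per setting. Rejection rates over the three slopes:

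- no shift: 0.050-0.052
- shift 0.25: 0.056-0.066
- shift 0.5: 0.065-0.120
- shift 1.0: 0.110-0.326

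**5. Could the planned A0 vs B0 comparison detect a shift?** Under the same assumptions the baseline SD is 1.8/√(2(1 − b)): 1.52, 1.80 and 2.32 for b = 0.3, 0.5 and 0.7. The standard error of A0 − B0 is SD × √(2/28) = SD × 0.267, giving 0.41, 0.48 and 0.62. A 0.5-point shift is only about 0.8 to 1.2 standard errors, so it cannot be told from chance imbalance.

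**6. Missing baselines.** The documents give no loss rate for the gap. If 5%, 10% or 20% of 60 left before POV2 (assumed; 20% is the SAP's allowance for attrition overall), 3, 6 or 12 ITT subjects would lack a baseline, leaving 57, 54 or 48. For them, only gender and age remain of the named predictors.

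**The case against.** The strongest reply is that bias is possible but not shown. Slope and shift are both assumed, and the documents give no sign. Against 3.0 points, 0.15-0.35 is small. The FUV1 SSQ12 is itself open-label self-report, where reporting bias would enter the estimate in full rather than scaled by a slope, and moving the baseline does not change that. All of this stands. It limits the weight of the point but does not justify leaving the covariate exposed.

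Several stronger readings are tempting but unsupported:

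- **That a shift could never be examined.** SAP 6.7.1.2 plans A0 vs B0 for SSQ12, and HHIE-S is taken at POV1 for eligibility, hence before randomisation. The first can hint at a shift, though it cannot separate one from chance. The second is a different scale but is a self-report taken before allocation.
- **That UCLA, GDS, LAQ and HUI-III suffer the same bias.** The mechanism is adjustment for baseline, and no SAP analysis of these scales adjusts for it. SAP 6.7.1.1 compares UCLA, GDS and HUI-III at A6 vs B6 with no baseline term stated. Their A0 values enter only exploratory comparisons, and LAQ appears in no listed analysis.
- **That subjects will leave on learning their arm.** Inclusion criterion 10 requires willingness to be randomised to either arm, and SAP 4.1 requires confirmed participation first. Some loss remains possible. Imputation could also fill a missing baseline, but the SAP does not say that it will.
- **That allocation could simply be withheld until after POV2.** Arm A surgery falls 1 week (± 1 week) after POV2, so only 0 to 2 weeks would remain to schedule it. That defeats the interval's stated purpose.

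**Conclusion.** The point holds as a weakness of design in the primary analysis. The sequence is clear from the documents: open-label randomisation at POV1, self-reported baseline SSQ12 2 to 8 weeks later, and use of that score in both the primary regression and the imputation. That known allocation could shift the score is an inference.

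For an assumed 0.5-point shift and slopes of 0.3-0.7, the bias is 0.15-0.35 points, or 5-12% of 3.0, in either direction. A reader might infer that the primary result is therefore unreliable, but the documents do not support that: if the true difference is near 3.0, a modest shift is unlikely to reverse the conclusion. One caution is that 3.0 is a before-and-after change in implanted patients. Using it as the between-arm difference assumes no change in controls. If controls improve, the same bias is a larger share of a smaller effect.

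The missing-baseline gap is a separate and definite omission from the SAP, of unknown size. The change is worth making because it is cheap and removes a possible bias from the primary estimate.

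**What to change.** - **Protocol sections 5 and 9.3.4:** give SSQ12 at POV1, after consent and before allocation is released, alongside the HHIE-S already taken there for eligibility.
- **SAP 6.1.2, 6.4 and 6.6.1.1:** define A0/B0 for SSQ12 as the POV1 score and use it as the covariate and the imputation predictor. Keep the POV2 score as descriptive or for a sensitivity analysis.
- **SAP 6.4:** state how an ITT subject with no baseline SSQ12 is handled.
- **Subjects already randomised without a POV1 SSQ12:** add a sensitivity analysis with POV1 HHIE-S as the pre-allocation covariate and imputation predictor. It is a weaker substitute, because it is a different scale and entry requires a score of at least 24, which narrows its range.

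The cost is a short amendment to each document and 12 extra items at an existing visit. The drawbacks are a baseline 2 to 8 weeks older and, for subjects supplied with hearing aids under Protocol 9.3.3, a rating that may precede adjustment to them. Keeping the POV2 score allows that to be examined. Sample size and the surgical timetable are unaffected.
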